cognitive or medical limitations per clinician report, (5) possess a cellphone, and (6) able to give consent. *Adolescents living with HIV (ALH) between the ages 12-17 will also be eligible to participate in focus groups and cognitive interviews as part of a separate component of the Development Phase. Their eligibility criteria is as follows:* (1) *read English and speak English or a local language spoken by clinic staff (e.g., Twi),* (2) *in medical care for HIV and receiving ART at our clinic,* (3) *aware of their HIV status as per parent/guardian report,* (4) *not impaired by cognitive or medical limitations per clinician report,* (6) *able to give assent, and* (7) *their parent/guardian is able to give consent. Parents or guardians of ALH are also able to participate in focus groups and cognitive interviews as part of this separate component. Parent eligibility is as follows:* (1) *speak English or a local language spoken by clinic staff (e.g., Twi),* (2) *own a mobile phone,* (3) *aware of their child's HIV status,* (4) *not impaired by cognitive or medical limitations per clinician report, and* (6) *able to give consent.* Participants in the randomized pilot must have also demonstrated a recent detectable viral load. Study staff will NOT make changes to ART regimens and participants will be encouraged to speak with their doctor if they have concerns about their medications or side effects of these medications. Any unexpected ethical issues that arise with our participants will be discussed immediately with the PI. All participants will receive a resource packet including information on ART as well as references to local health and social services. We will also encourage participants to identify a treatment monitor to take part in the game. This will not be a requirement for our study, however, because those who begin playing the game without a monitor will be incentivized via game rewards to recruit one (and we will assess this occurrence). Participants without a monitor will be assigned a peer educator to fill this role. Inclusion criteria for treatment monitors includes: 1) *read English and speak English or a local language spoken by clinic staff,* (2) *target HIV patient has agreed to their participation,* (3) *aware of target patient's HIV status as per patient report,* (5) *possess a cellphone, and* (6) *able to give consent.*

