Exclusion criteria. Individuals will be excluded if they meet any of the following criteria: (a) self-reported participation in another ART adherence-related study (YPLH only) or (b) unable to understand the consent process.

Sample, site/recruitment, and retention. We will recruit 24 YPLH and potentially 24 treatment monitors for the iterative open trial, and between 5-40 YPLH for the youth advisory group, as part of the Development Phase. The advisory board ranges from 5-40 participants because those who attend the first group meeting will be invited back to attend two to four additional meetings. However, if they are unable to attend, new participants will be added to the group. *We will also recruit 12-16 ALH and 12-16 parents/guardians of ALH for focus groups and 10 parent-ALH dyads for cognitive interviews, as part of the Development Phase.* Sixty 60 YPLH, and potentially 30 treatment monitors, will be recruited for the pilot. In the pilot, it is estimated that 70% of youth will be female given that females account for 58% of all HIV cases in Ghana and seek treatment more than males (5). About 25% of YPLH will be newly-initiated to ART. Efforts will be made to equally sample young people who acquired HIV perinatally and behaviorally. Site/recruitment: Participants will be recruited from the HIV care clinic (the Clinic) at the Komfo Anokye Teaching Hospital (KATH), a teaching hospital affiliated with the Kwame Nkrumah University of Science and Technology (KNUST) located in Kumasi. It is the second largest clinic in the country and has a patient population estimated at 4,000. Although no research activities involving human subjects will occur at Rhode Island Hospital (RIH; the co-PI's institution), RIH will support KNUST and KATH with compliance on regulatory matters, including authoring the standard operating protocol, IRB applications and approvals, quality control, and data analysis. Retention techniques: routinely updating contact information, reminder phone calls, online monitoring of game interactions, maintaining records of friend/family contacts, and obtaining an emergency contact.

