Measures: Participants' overall satisfaction with the game will be assessed using a modified version of the Client Satisfaction Questionnaire (CSQ-8) after each iteration. The CSQ is an 8-item measure with good reliability and validity and used previously with African samples (46). They will also complete a modified Session Evaluation Form (SEF), which has 13 items that reflect areas of feasibility and intervention utility. Participants will complete measures of main study outcomes using an audio-assisted computer self-interview (ACASI). Main outcome measures are listed in the next section. The last prototype will be reviewed and revised by the research team before being finalized. **Training of Research Assistants (RAs), Fidelity Monitoring, and Supervision:** RAs will be trained by the co-PI ([name]) over a period of two days to provide

game instructions. Game instructions will be audio-recorded and coded for fidelity. Problems with fidelity will trigger retraining of RAs by the PI. Peer educators will receive in-person supervision from study staff who will themselves receive Skype supervision from the [name]. [name] will also monitor participants' game activity daily via the system's website.

Randomized Controlled Pilot Phase (Aim 2)

We will evaluate the preliminary impact of the Text-Based Adherence Game run for one year compared to a control group. The pilot will include 60 YPLH on ART with the same eligibility criteria as the open trial. The same procedures will also be used pending open trial feedback. The game will be evaluated via a baseline and two follow-up assessments (6-/12-months post-baseline). Randomization will occur after enrollment using a random number generator. Participants not randomized to the Text-Based Adherence Game will receive the SOC condition as described above. See Figure 4.

Figure 4. Steps for Aim 2 Randomized Controlled Pilot

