Design Considerations. Mobile phones—access and confidentiality. Participants will need their own phones to enroll in the study. Participants are advised to password-protect their phones if possible yet many do not have this option. We will therefore (a) never send messages with identifying information or directly refer to HIV or HIV treatment, and (b) only enroll YPLH who agree to the risk of game messages being seen by others who use their phone. Phone numbers and de-identified patient information is securely stored in a HIPAA- compliant cloud database hosted by Dimagi. Only select study staff will be able to link participant names with ID numbers. Information will be stored and destroyed following HIPAA and IRB procedures (see Protection of Human Subjects). Assessments: Assessments will take 1 hour to complete and be administered in a private room in the Clinic using ACASI at baseline and 6- and 12-months post-baseline. Clinic records will also be coded for biologic outcomes and clinic visits at these

assessments. Participants will be remunerated 40 Cedis (\$8) for each one. They will also be given 80 Cedis worth of prepaid phone credits to send and receive text messages at the baseline and first follow-up assessments.

Measures: The measures below will evaluate HIV-related health functioning, knowledge, attitudes, and behavior. Measures previously used in Ghanaian or SSA

adolescent or young adult samples were chosen when possible. If necessary, revisions to measures will be made based on formative work to ensure cultural relevancy. **Primary**

Outcomes: Past 30-day adherence will be assessed using a 3-item measure recently developed via intensive cognitive interviewing and field tests (47) and validated against electronic drug monitoring(48) . Self report of four day ART adherence based on percent of doses taken will also be assessed using the AACTG questionnaire (49). Staff will abstract from the clinic record number of medical visits kept and missed in the past 6 months(50), and most recent HIV viral load measurement, CD4 count, and current ART schedule. See Appendix 2 for data extraction form. If viral load was not measured in the past 3 months, it will be assessed at this visit as part of routine clinical care. **Secondary**

[figure not shown]
Outcomes: Figure 5 presents an assessment schedule for each aim and describes the secondary outcomes. Appendix 3 contains questionnaire.

Data Analytic Plan

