Hypothesis One (Aim 1). The Text-Based Adherence Game will be feasible, appealing, and useful. YPLH in the third open trial iteration of the Text-Based Adherence Game will show shifts in primary and secondary outcomes in the expected directions from pre-post assessments.

Hypothesis Two (Aim 2). Compared to participants in the control group, participants in the Text-Based Adherence Game will show at 6 and 12 months post-intervention: improved ART adherence, clinic attendance, biologic functioning (lower

Figure 5. Assessment Schedule

HIV viral load, higher CD4 count), and shifts in secondary outcomes (social support, self-efficacy, etc.) consistent with adherence promotion. Repeated measures ANCOVAs will be used to test differences over time between study conditions on each outcome variable. Missing data will be handled using multiple imputation. Potential imbalance between treatment conditions on baseline characteristics will be addressed using inverse probability of treatment weights (51). Power: As this is a pilot study and the impact of the intervention is not known, there may not be adequate power to determine its efficacy; also, pilot studies are not designed to provide accurate estimates of effect sizes upon which to base large trials(52). However, the small pilot may provide a “signal” of impact on its primary outcomes and we will examine the effects of the intervention on secondary outcomes based on Social Action Theory. We assume that retention over one year is at least 86% based on past studies conducted in Ghana (31, 53) thus 52 cases of the 60 enrolled in the pilot are available for analysis. Power analyses were run with G*Power 3(54). The model assumed 3 assessments with 52 individuals. The analyses with alpha of 0.05 and power 0.80 will be able to detect small to medium effects.

DISSEMINATION OF RESULTS

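### The pilot states no ratio, blocking or stratification for 60 people; stratifying allocation by newly initiated versus established ART is a cheap guard against a chance imbalance in viral load

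*Combined protocol and SAP*

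**What the plan says.** The allocation method is one sentence in the section Randomized Controlled Pilot Phase (Aim 2): "Randomization will occur after enrollment using a random number generator". The text available gives no ratio, arm sizes, blocks, strata or concealment. Figure 4, which sets out the pilot steps, could not be read.

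Four other places bear on it:

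- **Sample, site/recruitment, and retention:** "About 25% of YPLH will be newly-initiated to ART". The same paragraph mentions that "potentially 30 treatment monitors, will be recruited for the pilot".
- **Inclusion criteria:** "Participants in the randomized pilot must have also demonstrated a recent detectable viral load".
- **Measures, Primary Outcomes:** staff abstract from the clinic record the "most recent HIV viral load measurement, CD4 count, and current ART schedule", alongside self-reported adherence and clinic visits.
- **Data Analytic Plan, Hypothesis Two:** repeated measures ANCOVAs are the main analysis, and any baseline imbalance between conditions is to be handled by inverse probability of treatment weights. Covariates are named for neither.

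Appendix 2, item 19, records the date of ART initiation, so time on ART is already collected.

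**The concern.** Everyone in the pilot enters with a detectable viral load, but for two different reasons. Some have only just started ART; others are detectable despite established treatment. The first group may well show a larger fall over the year whichever arm they are in. Baseline viral load alone may not separate the two groups, because both start detectable.

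If the roughly 15 newly initiated participants fall unevenly between arms, the viral load comparison (and CD4 with it) picks up part of that difference. The plan says the pilot may give a signal on its primary outcomes, and the executive summary intends the pilot data to support funding for a larger trial. A chance split of this kind could create such a signal or hide a real one. Allocation is the one stage at which this can be prevented rather than repaired.

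**Working it through.** **Inputs from the documents.** 60 randomised; about 25% newly initiated, so 0.25 × 60 = 15 newly initiated and 45 established; retention of at least 86%.

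**Inputs assumed.** A 1:1 ratio (not stated); an extra viral load fall in the newly initiated of 1 to 3 log10, with 2 as the middle value (no figure in the documents).

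**1. The plan's own figure.** 60 × 0.86 = 51.6, which rounds to the stated 52. It reproduces and is not in dispute.

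**2. Arm sizes, if allocation is simple 1:1.** With X ~ Binomial(60, 0.5):
- P(35:25 or worse) = 2 × P(X ≤ 25) = 24.5%
- P(36:24 or worse) = 2 × P(X ≤ 24) = 15.5%

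The consequence is small. Relative standard error at 35:25 is √[(1/35 + 1/25) / (1/30 + 1/30)] = √(0.06857 / 0.06667) = 1.014, a rise of about 1.4%. A two-arm comparison of 52 people with 80.0% power at equal arms (standardised difference 0.79) has 78.9% at a 35:25 ratio and 75.2% even at 40:20.

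**3. Split of the 15 newly initiated.**

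| Allocation | 10:5 or worse | 11:4 or worse |
|---|---|---|
| Simple 1:1, Binomial(15, 0.5) | 30.2% | 11.8% |
| Exactly 30:30, unstratified, hypergeometric(60, 15, 30) | 23.3% | 7.2% |
| Blocks of 4 within the two ART strata (simulated) | 0% (split always 7:8) | 0% |

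For the first cell: 2 × (1 + 15 + 105 + 455 + 1365 + 3003) / 2^15 = 9888 / 32768 = 30.2%. These probabilities count both directions; half of the uneven splits favour each arm.

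The second row shows that equalising the arms does not equalise the newly initiated. In the third row, arms came out at 29 to 31, and the share of newly initiated differed by at most 3.3 percentage points. With block sizes varying between 4 and 6, a stratum can be at most 3 apart (halfway through a block of 6), so the worst split of 15 is 9:6.

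**4. Effect on viral load.** With 30 per arm and a 10:5 split, the shares are 10/30 and 5/30, a difference of 5/30 = 0.167. The shift in the unadjusted difference is 0.167 × extra fall:
- extra fall 1 log10: 0.17 log10
- extra fall 2 log10: 0.33 log10
- extra fall 3 log10: 0.50 log10

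The probability that goes with this example is 23.3%, because it fixes the arms at 30:30.

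**5. How unusual that shift is.** At an extra fall of 2 log10, this component alone has standard error √[2² × 0.25 × 0.75 × (1/30 + 1/30)] = √0.05 = 0.22 log10. A shift of 0.33 is therefore about 1.5 standard errors.

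**6. What the weights would do.** In a 10:5 split, weighting on this factor alone gives 15/10 = 1.5 to each newly initiated person in the larger group and 15/5 = 3 to each in the smaller. At 11:4 the latter becomes 15/4 = 3.75. The correction then leans on four or five people.

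**The case against.** The strongest reply is that the plan already handles this. It is silent on restriction rather than opposed to it, and a random number generator can just as well produce a blocked list. The analysis is not unadjusted: it combines ANCOVA with weights for baseline imbalance, and the ART start date is available to enter either. The weights use baseline data on all 60 randomised, not only the 52 expected to complete. Chance imbalance under random allocation is not bias; step 5 shows an ordinary amount of sampling variation, which an unadjusted standard error already carries. The choice of stratum is also open to debate: the plan comments on sex and route of infection too, and the argument does not clearly reach adherence or clinic visits. Finally, the plan itself says that power may be inadequate.

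Most of this stands, and it limits the point to a cheap improvement. It does not remove it. No covariate is named, so nothing commits the analysis to balancing time on ART, and choosing covariates after seeing the imbalance adds discretion. Weights are also a fragile repair when four or five people carry them.

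A reader might infer several stronger claims that the documents do not support:

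- **That the plan adopts simple randomisation.** It states no method beyond the generator.
- **That it assumes 30 per arm and so contradicts itself.** The mention of 30 possible treatment monitors only suggests that number.
- **That viral load in the newly initiated is expected to fall regardless.** This is a reasonable inference, but no section says it or gives a size, and newly initiated is not defined.
- **That unequal arms threaten the pilot's precision.** Step 2 shows that they hardly matter.

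**Conclusion.** The point holds as a cheap improvement. No ratio, blocking or stratification is stated, and the planned remedy for imbalance has no named covariates. If allocation is simple 1:1, there is a 30% chance that the newly initiated split 10:5 or worse; with 30:30 arms and no strata the chance is 23%. At 30 per arm, a 10:5 split would move the unadjusted viral load difference by 0.17 to 0.50 log10.

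The probabilities rest on exactly 15 newly initiated and a 1:1 ratio. The log10 range rests entirely on the assumed extra fall of 1 to 3 log10. The loss is one of precision and interpretability in a small pilot; calling it systematic bias would be wrong. If a stratified list is already intended, all that is needed is to say so.

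**What to change.** In the Aim 2 section, state that allocation is 1:1 from a computer-generated permuted-block list with varying block sizes (for example 4 and 6). Stratify it by newly initiated versus established on ART, prepare it away from the clinic and conceal it until each participant is enrolled. Define newly initiated by a cut-off in time since ART start, and abstract Appendix 2, item 19, before allocation.

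In the Data Analytic Plan, pre-specify that stratum and the baseline value of each outcome as covariates in the repeated measures ANCOVA, with 6 and 12 months as the outcome visits. If the weights are kept, list their covariates in advance.

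The cost is a few sentences and a prepared list; no new data are needed. The small downside is some predictability at block ends in a single-clinic pilot whose arms are evident to participants and staff. Varying the block size and concealing the list limit this.

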Appendix 2: Chart Review Data Abstraction Form

1) Today's date:
(MM)_____(DD)_____(YY)_____

2) Date of first presentation to KBTH:
(MM)_____(DD)_____(YY)_____

3) Age (years) _____

4) Gender
 1 – Male
 2 – Female

5) Marital Status
 1 – Single
 2 – Married
 3 – Divorced
 4 – Separated
 5 – Cohabiting
 6 – Not Available

6) Highest education level attained
 1 – None
 2 – Primary
 3 – JSS
 4 – MSLC
 5 – Sec/Tech
 6 – University

7) Employment/occupation at presentation

8) Employment status at presentation
 1 – Full time
 2 – Part time
 3 – On leave
 4 – Unemployed
 5 – Unknown

9) Dependent children (aged <18 years)
 1 – Total number

 2 – How many are HIV+

10) Funding type
 1 – Patient out-of-pocket
 2 – Medical insurance
 3 – Special project
 4 – Employer sponsored
 5 – Unknown
 6 – Other: _____

11) HIV status at presentation:
 Known positive
 Diagnosed at admission

12) Current WHO stage
 1 – Stage I
 2 – Stage II
 3 – Stage III
 4 – Stage IV

13) Current Drug Therapy (check all that apply):
 1 – Stavudine
 2 – Zidovudine
 3 – Lamivudine
 4 – Abacavir
 5 – Tenofovir
 6 – Didanosine
 7 – Nevirapine
 8 – Efavirenz
 9 – Combivir (zidovudine and lamivudine)
 10 – Kaletra (lopinavir/r)
 11 – Nelfinavir
 13 – Other:

14) Most recent CD4 cell count: _____

15) Date of most recent CD4 cell count test:

16) Most recent viral load: _____

17) Date of most recent viral load test:

18) Detectable viral load in past six months:
 – Yes
 – No

19) Date of ART initiation:
(MM)_____(DD)_____(YY)_____

20) Number of clinic appointments missed in the past 6 months

21) Number of clinic appointments kept in the past 6 months

22) Number of clinic appointments missed in the past 12 months

23) Number of clinic appointments kept in the past 12 months

24) Longest period without an appointment (months):

25) Route of HIV infection
 1 – Perinatal
 2 – Behavioral
 3 – Unknown

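### The primary attendance outcome is a six-month look-back from each clinic assessment with no anchor at randomisation, so a late or early assessment shifts the period scored

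*Combined protocol and SAP*

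**What the plan says.** The combined protocol and SAP lists attendance among the primary outcomes (Randomized Controlled Pilot Phase, Measures): "Staff will abstract from the clinic record number of medical visits kept and missed in the past 6 months". The Assessments text in the same section ties the count to the visits: "Clinic records will also be coded for biologic outcomes and clinic visits at these" assessments, which are "administered in a private room in the Clinic using ACASI at baseline and 6- and 12-months post-baseline". The schedule itself is stated as "The game will be evaluated via a baseline and two follow-up assessments (6-/12-months post-baseline", and on allocation the text says "Randomization will occur after enrollment using a random number generator".

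The chart form (Appendix 2) opens with the date on which it is filled in (item 1). It then asks for "Number of clinic appointments missed in the past 6 months" and the matching number kept (items 20–21). It also asks for "Number of clinic appointments missed in the past 12 months" and the matching number kept (items 22–23). It has no field for the randomisation or baseline date.

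The text provided contains no visit window and no rule for late or early assessments. On analysis, the Data Analytic Plan says "Repeated measures ANCOVAs will be used to test differences over time between study conditions on each outcome variable".

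**The concern.** A six-month look-back matches months 0–6 and 6–12 only for a participant assessed exactly on time. Otherwise the period scored moves with the visit. Because the visit takes place at the clinic, a lapse in attendance can itself delay it, so the measurement window can depend on the behaviour being measured.

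Lateness could also differ by arm. The Literature Review names clinic visit reminders among possible game components, and the retention techniques include online monitoring of game interactions, which can apply only to the game arm.

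There is a related issue at baseline. The outcome is stated as a number of visits. A participant in care for less than six months has few visits because of short exposure, and the count then rises in either arm. The protocol expects about 25% of participants, that is 0.25 × 60 = 15, to be newly initiated on ART, although new to ART is not the same as new to the clinic.

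At stake is the meaning of one primary outcome in a pilot that looks for a signal on its primary outcomes and will be used to seek funding for a larger trial.

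**Working it through.** **Inputs.** The look-back of 6 months is from Primary Outcomes and Appendix 2. Assessments planned at months 6 and 12 are from the pilot section. Actual assessment dates, monthly appointments and the pattern of misses are assumptions, since the documents give none of them. Month 0 is taken as both baseline and randomisation.

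**The plan's own figures.** The plan gives no figure for lateness. Its retention figure (86% of 60 = 51.6, stated as 52) reproduces, but it concerns how many participants are analysed, not when they are assessed.

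**Formula.** An assessment at month A scores the interval (A − 6, A]. With follow-ups at A1 and A2:
- opening months left out = A1 − 6, if positive; if negative, its size is the pre-randomisation time brought in
- time entering both values = 6 − (A2 − A1), if positive
- time lost between the windows = (A2 − A1) − 6, if positive

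| A1 / A2 | Months scored | Left out of 0–12 | In both values |
|---|---|---|---|
| 6 / 12 | 0–6, 6–12 | none | none |
| 7 / 12 | 1–7, 6–12 | 0–1 | 6–7 |
| 8 / 12 | 2–8, 6–12 | 0–2 | 6–8 |
| 9 / 13 | 3–9, 7–13 | 0–3 | 7–9 |
| 9 / 15 | 3–9, 9–15 | 0–3 | none |
| 6 / 14 | 0–6, 8–14 | 6–8 | none |
| 5 / 12 | −1 to 5, 6–12 | 5–6 | none |

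A two-month delay moves 2/6 = 33% of the window. A two-week delay moves about 0.5/6 = 8%.

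**Effect on the outcome values.** Take appointments at months 1 to 12, with 5, 6 and 7 missed, and assessments at months 8 and 12.
- First follow-up, look-back (appointments 3–8): 3 missed, 3 kept. Fixed window (1–6): 2 missed, 4 kept.
- Second follow-up, either rule (7–12): 1 missed, 5 kept.

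Only the first value changes, from 2 to 3 missed. As a proportion kept, it goes from 4/6 = 67% to 3/6 = 50%.

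**Direction.** Take one appointment in the middle of each month and assessments at months 9 and 12.
- All missed in months 6–9: the look-back gives 3 then 3; fixed windows give 0 then 3.
- All missed in months 0–3: the look-back gives 0 then 0; fixed windows give 3 then 0.

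The same lateness overstates misses in one case and hides them in the other.

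**After the fix.** Windows (0, 6] and (6, 12] leave 0 months out and count 0 months twice, whatever the assessment dates.

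**The case against.** **The early months are still collected.** A reader might infer that they are never counted at all. The form does not support that. In the example, the month-12 form records 3 missed and 9 kept over 12 months, and 1 missed and 5 kept over 6 months. Subtraction gives 2 missed and 4 kept for months 1–6, exactly the fixed-window answer. This stands, with limits. The stated outcome is the six-month count, and no analysis uses the 12-month items. Recovery also needs the final form to be on time: completed at month 14, subtraction returns months 2–8.

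**The total is not what is analysed.** A reader might add the two values and report 4 misses against 3. The repeated measures ANCOVA treats each assessment as its own value, so that total is never formed.

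**The anchor is partly inferred.** The Participant Involvement text places chart review at baseline, 6 and 12 months post-baseline, which could mean scheduled dates, and a chart can be read without the patient present. Figures 4 and 5 are not shown, so a timing rule there cannot be excluded. But the schedule wording supplies neither a window nor an anchor, and an abstractor holding this form has only its completion date to count back from.

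**Lateness may be small.** Reminder calls, updated contact details and family or friend contacts are planned, and may keep assessments near schedule. Two equally late follow-ups produce no double counting.

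**The proportion is obtainable.** Visits kept and missed are both abstracted, so the ratio needs no new data. The text does not say which form is analysed. A count that rises in either arm because of short baseline exposure does not by itself bias the comparison between arms.

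**Conclusion.** The point holds as a weakness in how a primary outcome is defined. Followed as written, the attendance window moves with the assessment date, and that date can depend on attendance. Loss of the opening months needs a late first follow-up; time entering both values needs follow-ups less than six months apart; pre-randomisation time enters when the first follow-up is early.

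In the illustration, the first follow-up value changes by one missed visit and the second does not change. That size rests on assumed monthly appointments and an assumed two-month delay. The documents give neither the amount of lateness nor any difference between arms.

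A reader might also infer that lapses are over-counted in whichever arm lapses more, and hence that the sign of the bias is known. The documents do not support this: early lapses can drop out of the outcome altogether, so the direction is open. The change is worth making because it is cheap and removes the dependence, not because a bias of known size has been shown.

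**What to change.** - Add the randomisation date to the Appendix 2 form.
- In the Measures section, define attendance by calendar date: appointments kept and missed from randomisation to month 6, and from month 6 to month 12, whatever the date of the assessment.
- Analyse kept/(kept + missed) in each window. Limit the baseline value to the part of the preceding six months in which the participant was in care; the form's dates of first presentation and ART start (items 2 and 19) help identify short exposure.
- State a visit window for the assessments, and say what role the 12-month items (22–23) play.

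The cost is a form edit and a short addition to the Measures text. The abstractor uses the same chart, with no extra visits or participants. The one practical burden is that when an assessment is held early, the chart must be reopened once the window has closed.
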